#### **2- Study drug dose modifications for increases in ALT and/or AST**

Cases of idiosyncratic Drug-Induced Liver Injury (DILI) with increases in ALT and/or AST to  $\geq 5$  and  $\geq 20$ x ULN, including with concomitant bilirubin elevation  $> 2$ x ULN, have been reported with darolutamide.

Liver function test (LFT) abnormalities were reversible upon darolutamide discontinuation.

In case of hepatic transaminase elevations suggestive of idiosyncratic Drug Induced Liver Injury (DILI) considered to be causally related to darolutamide, treatment with darolutamide should be permanently discontinued. More specific guidance on how to proceed in the case of DILI is provided in the protocol in section 5.5 dose adaptation.

In the event of treatment interruption due to toxicity of more than 56 days, the decision to restart treatment or not should be discussed and agreed between the Investigator and Sponsor.

Dose reduction below 300 mg b.i.d. is not recommended, because efficacy has not been established.

## E) STATISTICAL ANALYSIS PLAN

### REQUIRED NUMBER OF PATIENTS TO BE SCREENED/INCLUDED:

Assuming a median rPFS of 12 months for the control group (based on data from the control arm of the LATITUDE trial ([Fizazi, 2017](#)), and taking into account that 1) patients with oligo-metastatic disease (low risk patients) will not be in this group, and 2) some patients are expected to die from other causes before they reach a progression endpoint, making the median rPFS probably shorter than what it was in the LATITUDE trial), a planned sample size of 300 subjects will be required to provide an 85% power to detect at least a HR of 0.65 (median rPFS 12 months in the standard arm versus 18.5 months in the experimental arm) at a 2-tailed significance level of 0.05 and a drop-out hazard rate in both arms of 0.014 (i.e. a maximum 19.3% drop-out rate at the end of study corresponding to non-evaluable or study withdrawal patients).

The number of **randomised patients will be 300 patients** (150 patients per arm). The dropout rate will be monitored during the study and in case of increased drop-out the sample size may be adjusted accordingly.

#### STATISTICAL ANALYSIS:

For primary and secondary efficacy endpoints, the analysis will be performed on the ITT population, i.e. all randomised patients will be included, whether eligible or not, compliant or not. Patients will be analysed according to their randomisation arm, regardless of the actual treatment received.

Analysis of the primary endpoint will be event-driven. Time to event endpoints will be reported using the Kaplan-Meier method with Rothman's 95% confidence intervals. A log-rank test will provide the statistical significance of the randomised treatment effect. Additionally a Cox model will provide an estimate of the randomised treatment effect (hazard ratio).

Stratification factors will include: LATITUDE risk criteria (high risk versus low risk, [Fizazi, 2017](#)) and ECOG performance status score (0 or 1 vs. 2).

Qualitative data will be expressed as percentages and compared between the treatment groups using the chi-square test (or the Fisher exact test). Quantitative data will be expressed as means and standard deviation (or medians and range) and compared between the treatment groups using the Student t-test (or the Wilcoxon test).

The analysis of the secondary endpoints will be performed using a formal adjustment for multiple testing.

One interim analysis will be performed after observing at least 70% of the number of expected events (i.e. at least 138 events). Stopping rules using the spending function approach of Lan and DeMets with O'Brien-Fleming type spending function will be followed to conclude at each sequential analysis.

Nominal p values for overall type I error of 0.05 Lan-DeMets boundaries are:

- Efficacy interim analysis (138 events, i.e. 70% expected events): p-value to reject  $H_0 \leq 0.015$  (equivalent to the stopping boundaries Z-Scale:  $\pm 2.437$ )
- Final analysis (197 events, i.e. 100% expected events): p-value to reject  $H_0 \leq 0.045$  (equivalent to the stopping boundaries Z-Scale:  $\pm 2.0$ )

The results of the interim analyses will be given only to the IDMC members.

Safety analysis will be summarized on the Safety Population (i.e. all patients who receive any part of investigational treatment). Incidence of AEs will be summarized by system organ class and preferred term according to MedDRA coding, and will be presented by treatment groups and

overall. AEs will be summarized by grade (NCI CTCAE v5.0), according to the worst grade experienced.

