- (j) This information may be collected during onsite visits (as part of patients continued treatment at the site), via communication with the patients treating physician or via telephone contact with the patient.
- (k) The questionnaires must be completed before the initiation of treatment.
- (l) Paraclinical examination (CT scan or MRI and bone scan) to be performed within 12 weeks prior to randomization, but we strongly recommend that baseline imaging be performed within 28 days prior to randomization.
- (m) handgrip strength should be measured twice at each visit.

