### 3.4. Inclusion and randomisation procedure

Patients written informed consent is to be obtained before any study related procedures are performed. Candidates who consent to study participation will then enter the Screening period (max. 28 days prior to start of treatment) during which all examinations required to assess their eligibility will be performed, including demographic data collection, tumour evaluation and clinical and laboratory evaluations (see Section 7.1). The availability of a suitable formalin-fixed, paraffin-embedded (FFPE) biopsy sample of a metastatic site or primitive tumour tissue will be verified during the screening period. Blood samples will also be collected prior to the start of treatment.

Eligible patients will be randomised via the interactive web response system (IWRS, <https://ecrf.euraxipharma.fr/csonline/>) and registered on the Unicaner electronic case report form (eCRF, <https://ecrf.icm.unicancer.fr/csonline/>) with a unique identification number. This number must be used as the sole patient identifier throughout the study.

It is the responsibility of the investigator to verify and confirm that all inclusion and non-inclusion criteria are met prior to randomisation.

Eligible patients will be randomised (1:1) via a specific Interactive Web Response System (IWRS) to receive either:

- Experimental arm: ADT + darolutamide 600 mg po b.i.d.
- Control arm: ADT + placebo po b.i.d.

Randomisation will be blinded, and stratified according to LATITUDE risk criteria (high risk versus low risk) and ECOG performance status score (0 or 1 vs. 2) using a system of different sized random permuted blocks to ensure the treatment arms are balanced for all combinations of stratification factors. A patient is considered as high risk according to the LATITUDE criteria if he has at least two of the three following high-risk factors associated with poor prognosis: a Gleason score of 8 or more (on a scale of 2 to 10, with higher scores indicating more aggressive disease), at least three bone lesions, and the presence of measurable visceral metastasis. He is otherwise considered as low risk ([Fizazi, 2017](#)).

E-mail confirmation of the randomisation and assigned treatment number will be sent to the Investigator, Statistician, Sponsor and Data Manager.

Instructions for the use of the IWRS will be provided to all investigators during the trial initiation visit at each site.

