### 7.3. Visits and assessment during treatment period

#### 7.3.1. Visit 1 - Day 1 (Treatment start)

Study treatment should be initiated within 24 hours of randomisation.

The following should be performed prior to the administration of IP:

- Assessment of ongoing toxicities including pre-existing symptoms and any concomitant therapies received.
- Assessment of patient quality of life (before initiation of treatment) using the following tools:
  - EORTC-QLQ-C30 (Appendix 10)
  - EORTC QLQ-PR25 (Appendix 11)
  - BPI-SF (Appendix 12).
- **French Investigational sites only – For patients who provide additional informed consent:** Collection of blood samples for translational analyses (to be performed prior to treatment initiation - see Section 9.1.1).
- **Patients who provide additional informed consent:** Abdominal circumference, body mass index (BMI) and maximum handgrip strength using a hand dynamometer. Handgrip strength should be measured twice.
- Dispensation of treatment for 30 days

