The proportional hazard assumption will be assessed graphically by plotting log (-log[estimated survival distribution function]) against log(survival time). The resulting graphs should have approximately parallel lines when the assumption holds. If the proportional hazards assumption is reasonably met, then a stratified Cox proportional hazard model will be used to estimate the treatment effect using Hazards Ratio (HR) and its two-sided 95% confidence interval (95%CI). If the proportional hazards assumption is violated, then the inference remains statistically valid for testing equality in survival distributions. In addition, rPFS will be descriptively summarized using Kaplan-Meier methodology, including medians and two-sided Rothman's 95%CI ([Kaplan, 1958](#); [Rothman, 1978](#)).

Stratification factors will include:

- LATITUDE risk criteria (high risk versus low risk, [Fizazi, 2017](#))
- ECOG performance status score (0 or 1 vs. 2).

If final analysis of the primary endpoint meets the pre-specified hypothesis (see Section 10.1), an additional sensitivity analysis of rPFS will be performed using the results of a centralised disease evaluation by an independent review committee (IRC).

All the other secondary time to event endpoints (namely, CRPC-free survival, clinical progression-free survival, time to worsening in prostate cancer-related urinary symptoms, time to next symptomatic skeletal event, prostate cancer specific survival and overall survival, time to first subsequent SACT and time to second subsequent SACT) will be analysed using the same methods as the primary endpoint (stratified two-sided log-rank test, stratified Cox proportional hazards models). Secondary endpoints will be analysed according to the investigators' assessment of response. Censoring rules for these endpoints will be detailed in the SAP.

The median follow-up will be estimated using the inverse Kaplan-Meier method ([Schemper, 1996](#)).

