#### **10.3.4. Quality of life analysis**

The expectation is that changes in patient quality of life will not differ significantly between the two treatment groups. Changes in patient quality of life over time will be investigated with particular attention paid to the following characteristics: Physical function, cognitive function, and fatigue (EORTC-QLQ-C30), pain (BPI-SF) and urinary symptoms (EORTC-QLQ PR25).

Detailed hypotheses will be developed in the statistical analysis plan (SAP).

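### The tests named for scores and binary endpoints use neither the collected baseline values nor the randomisation strata; only exploratory comparisons are affected

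*Protocol*

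**What the plan says.** The statistical analysis paragraph of the protocol summary (part E) gives one general rule for data that are not time-to-event. Quantitative data are "compared between the treatment groups using the Student t-test (or the Wilcoxon test". Qualitative data are "compared between the treatment groups using the chi-square test (or the Fisher exact test".

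Elsewhere the protocol provides for what those tests leave out:

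- Section 3.4: randomisation is "stratified according to LATITUDE risk criteria (high risk versus low risk) and ECOG performance status score (0 or 1 vs. 2".
- Section 10.3.2: the listed secondary time-to-event endpoints use the methods of the primary endpoint ("stratified two-sided log-rank test, stratified Cox proportional hazards models").
- Section 7.3.1, for Day 1 before study drug: "Assessment of patient quality of life (before initiation of treatment) using the following tools". A footnote to the schedule of visits adds: "The questionnaires must be completed before the initiation of treatment". Section 7.1 places the G-CODE at screening.
- Section 10.3.4: "Changes in patient quality of life over time will be investigated with particular attention paid to the following characteristics". It names no test and leaves the detailed hypotheses to the SAP. Section 10.3.5 describes change over time in ADL, IADL and other geriatric parameters, again without a test for the scores themselves.
- Section 10.3.7: endpoints other than the primary and key secondary ones are exploratory, each tested at two-sided 0.05.

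**The concern.** The trial randomises within LATITUDE risk and ECOG and carries both factors into its listed time-to-event analyses. It then names tests without those factors for everything else. Urinary symptoms, for example, would be analysed with the strata as a time to worsening, but without them if the score were compared under the summary's rule.

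If the strata are prognostic, a test that ignores them after stratified randomisation overstates the variance of the treatment comparison. A two-sample test on a follow-up score also discards the patient's own baseline value and leaves any chance baseline imbalance in the estimate.

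What is at stake is precision. Section 10.3.4 expects quality-of-life changes not to differ significantly between arms. Where that is the expected result, an inefficient test makes it easier to obtain, and tolerability is part of the case for the drug in this frail population.

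**Working it through.** **The plan's own figure.** There is none for these endpoints: no SD, correlation, effect size or power. The 300 patients, 85% power and 197 events in section 10.1 belong to rPFS. They reproduce approximately (194 events by Schoenfeld's formula, 200 by Freedman's) but do not bear on this point.

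**Inputs from the protocol.** 150 per arm; two-sided 0.05; a maximum drop-out of 19.3%, which leaves 150 × (1 − 0.193) ≈ 121 per arm; and the half-SD threshold for deterioration on QLQ-PR25 subscales in section 3.2.2.

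**Assumptions.** Unadjusted power of 80%; correlation ρ between baseline and follow-up of 0.3, 0.5 or 0.7; roughly normal scores with equal variance.

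**Step 1: difference that gives 80% unadjusted power.** d = (1.960 + 0.842) × √(2/150) ≈ 0.32 SD.

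**Step 2: effect of the baseline covariate.** ANCOVA multiplies the variance by (1 − ρ²), so power = Φ[(1.960 + 0.842)/√(1 − ρ²) − 1.960]. A t-test on change scores multiplies the variance by 2(1 − ρ).

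| ρ | t-test on score | t-test on change | ANCOVA | ANCOVA minus t-test on score |
|---|---|---|---|---|
| 0.3 | 80% | 65.8% | 83.6% | 3.6 points |
| 0.5 | 80% | 80.0% | 89.9% | 9.9 points |
| 0.7 | 80% | 95.1% | 97.5% | 17.5 points |

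Worked line for ρ = 0.5: 2.802/√0.75 = 3.235; 3.235 − 1.960 = 1.275; Φ(1.275) = 0.899.

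A simulation of 4,000 trials at 150 per arm, ρ = 0.5 and the Step 1 difference gave 78.9% (t-test), 80.0% (change score), 76.9% (Wilcoxon) and 89.6% (ANCOVA).

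**Step 3: sensitivity to the 80% assumption, at ρ = 0.5.** Power = Φ[d/√(2/n) − 1.960], with d divided by √0.75 for ANCOVA.

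| n per arm | Difference | t-test | ANCOVA | Gain |
|---|---|---|---|---|
| 150 | 0.5 SD | 99.1% | 99.9% | 0.8 points |
| 121 | 0.5 SD | 97.3% | 99.4% | 2.1 points |
| 60 | 0.5 SD | 78.2% | 88.5% | 10.3 points |
| 150 | 0.3 SD | 73.8% | 85.1% | 11.3 points |

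**Step 4: strata and PSA response.** The gain from stratifying the binary test depends on the response rate and on how strongly LATITUDE risk and ECOG predict response. The protocol gives neither, so no figure can be attached. Steps 2 and 3 measure baseline adjustment of continuous scores only.

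**The case against.** The strongest objection is that the protocol does not commit quality-of-life or geriatric scores to a t-test. The sentence is generic summary text that names no endpoint. The same paragraph speaks only of a log-rank test where section 10.3.2 specifies a stratified one, so its silence on covariates is not a decision to omit them. Section 10.3.4 leaves the detailed quality-of-life hypotheses to the SAP. This stands in part: the SAP may hold a better model. The summary sentence is nevertheless the only between-arm test named for the scores and for PSA response, and it would then conflict with that SAP.

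A second objection is that baseline is not ignored everywhere. Clinical PFS, urinary worsening and PR25 deterioration are all defined relative to baseline, and the first two are analysed stratified. Section 10.3.5 also compares time to definitive ADL deterioration, measured against the score at inclusion, with a complementary competing-risks analysis. This stands. A reader might infer that the plan could conceal a real deterioration in function or symptoms; these endpoints are why the documents do not support so broad a reading.

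A reader might also infer a flat loss of 10 points of power. That needs both ρ = 0.5 and 80% unadjusted power, and the protocol sets neither. The half-SD threshold, where the gain is 1 to 2 points with 121 to 150 per arm, defines deterioration in a patient and is not a planned difference between arms, so it does not settle the size either. The normal-theory figures are also only a rough guide for ADL (0 to 5) and 4-IADL (0 to 4).

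Finally, omitting balanced strata makes a test conservative, not invalid. That is correct.

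**Conclusion.** The point holds as a minor matter of efficiency and consistency. The only tests named for continuous scores and binary endpoints use neither the baseline values nor the strata, both of which are already collected. The affected comparisons are exploratory under section 10.3.7. The primary and key secondary efficacy endpoints are time-to-event and stratified, so nothing here supports a reading that the trial's main inference is at risk.

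The gain from baseline adjustment is 3.6 to 17.5 points of power for ρ between 0.3 and 0.7, if unadjusted power is 80% with 150 per arm. It is much smaller where the unadjusted test is already well powered. All of these sizes rest on assumed correlations and effects, and none can be given for the strata or for PSA response.

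**What to change.** Replace the generic sentence in part E of the summary and put matching wording in sections 10.3.4 and 10.3.5:

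- Compare continuous quality-of-life and geriatric scores at a stated visit by ANCOVA, with treatment arm, baseline value, LATITUDE risk and ECOG as terms.
- A repeated-measures mixed model is optional. If it is used, state its missing-at-random assumption. QLQ-C30, QLQ-PR25 and G-CODE have no assessments in long-term follow-up, and treatment ends for progression, toxicity or patient choice, so that assumption needs to be visible.
- Compare complete PSA response at 6 months with a Cochran-Mantel-Haenszel test stratified by LATITUDE risk and ECOG.
- Keep the t-test/Wilcoxon and chi-square/Fisher tests as descriptive support.

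The cost is protocol and SAP wording only. The baseline scores and both stratification factors are already collected, so no visit, sample or patient is added. If the SAP already specifies such models, only the summary sentence needs to be aligned with it.

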## F) OPTIONAL TRANSLATIONAL RESEARCHES

### 1. Samples

Blood samples and tumour tissues will be collected to conduct a translational program to address two current critical questions:

- (i) What are the oncogenic drivers of *de novo* metastatic prostate cancer?
- (ii) What is the underlying biology of oligometastatic prostate cancer?

*De novo* metastatic patients have a poor prognosis and contribute to at least 50% of prostate cancer-related deaths. The landscape of genomic alterations in M1 prostate cancer remains uncharacterized. Specifically, we hypothesize that molecular drivers usually found later during disease evolution when patients develop resistance to castration may be already present in M1 prostate cancer.

#### Tumour samples

The following samples will be collected from all patients who provide their additional consent:

- Archived Formalin fixed / paraffin embedded (FFPE) biopsy material obtained at time of diagnosis as part of the standard medical care will be collected at study entry.
- Where feasible, a biopsy will be performed at time of disease progression to collect a treatment-resistant tumour sample.

#### Blood samples (France only)

Blood samples will be collected prospectively during the study from patients who provide their additional consent, in order to study tumour clonal evolution. At Day 1, prior to initiating IP treatment, blood will be collected from each patient and processed to obtain circulating tumour cells (CTCs) and plasma. An additional sample of whole blood will also be collected for genomic analysis.

Additional blood samples will be collected and processed to obtain CTCs and plasma at Day 30 (plasma), Day 60 (CTCs), Day 120 (plasma), and at disease progression (CTCs and plasma).

#### Exome analysis

Host and cell-free tumour DNA will be extracted from baseline blood samples (whole blood and plasma). Archival FFPE biopsy samples will be used to extract somatic tumour DNA.

Both normal and somatic DNA will be then used for whole-exome sequencing in order to investigate (a) the genomic landscape (single nucleotide variation [SNV], copy number variation [CNV]) of M1 prostate cancer (b) the tumour clonal evolution in a subset of patients in whom paired biopsies (baseline – resistant tumour) are available. Cell-free DNA collected at baseline and at progression will be analysed in order to assess clonal evolution.

### ***Transcriptome analysis***

RNA will be extracted and analysed using TruSeq RNA/exome technology (Illumina) for mRNA profiling. TruSeq RNA/exome technology which generate RNA sequencing libraries from degraded samples that focus on the RNA coding regions. The TruSeq RNA/exome system isolates the high-value content regions to maximize discovery power with low input requirements and is extensively validated.

### ***Immunohistochemistry***

Immunohistochemistry staining will be performed on serial FFPE tumour tissue slides. Eleven markers will be assessed to identify key phenotypes of prostate cancer (AR, PSA, ERG, synaptophysin, chromogranin A, CD56, PTEN, p53, Rb, Ki67, SPOP).

### ***Circulating tumour cells***

Given the risk of tumour heterogeneity, samples from biopsy may not capture all tumour characteristics. Blood assays thus will be developed to investigate tumour-based biomarkers on CTCs. The objectives of this ancillary CTC analysis are to:

- Develop and validate a non-invasive and multiparametric assay to predict response to androgen receptor inhibitor through the detection and monitoring of neuroendocrine and genome instability markers-positive CTCs.
- Evaluate the relevance of this assay for patient stratification according to rPFS and OS.

Whole blood samples will be processed to obtain CTCs and control white blood cells by hematopoietic blood-cell depletion and cell sorting. Whole-genome amplification (WGA) will be performed and copy number alterations analysed on CTC and control white blood cell WGA samples using the LowPassGenome technique.

## **2. Sarcopenia**

Additional data will be collected for consenting patients in order to answer the following secondary objective: what is the impact of sarcopenia on survival and treatment response?

A complementary clinical evaluation will be performed by investigators and recorded in the eCRF at each timepoint, from Screening to End of treatment:

- Abdominal circumference, weight and height and body mass index (BMI)
- Maximum handgrip strength using a hand dynamometer (handgrip strength should be measured twice at each visit.)

In addition, CT images from centres participating in the ancillary study will be used to measure skeletal muscle index.

